4 IDENTITY OF INVESTIGATIONAL PRODUCT

The Investigational Medicinal Product (IMP) will be supplied as TBAJ-876 Oral Suspension, 5 mg/mL formulation or matching placebo, TBAJ-876 tablets 25 mg, and TBAJ-876 tablets 100 mg.

Refer to Appendix 2 for details regarding the description and composition of TBAJ-876 oral suspension, TBAJ-876 tablets 25 mg, and TBAJ-876 tablets 100 mg.

Table 7 Identity of Investigational Products

Test Products:	TBAJ-876 Oral Suspension 5 mg/mL			
	Manufactured for Global Alliance for TB Drug Development			
	TBAJ-876 Tablets 25 mg			
	Manufactured by Piramal Pharma Limited for Global			
	Alliance for TB Drug Development			
	TBAJ-876 Tablets 100 mg			
	Manufactured by Piramal Pharma Limited for Global			
	Alliance for TB Drug Development			

Control Product:	Placebo for TBAJ-876 Oral Suspension
	Manufactured for Global Alliance for TB Drug Development

5 SUBJECT SELECTION

5.1 Inclusion Criteria

All volunteers must satisfy the following criteria to be considered for study participation:

- 1. Understands study procedures and voluntarily provides written informed consent prior to the start of any study-specific procedures.
- 2. Is a healthy adult male or female, 19 to 50 years of age (inclusive) at the time of screening.
- 3. Has a body mass index (BMI) \geq 18.5 and \leq 32.0 (kg/m²) and a body weight of no less than 50.0 kg at the time of screening and check-in.
- 4. Is medically healthy with no clinically significant screening results (e.g., laboratory profiles normal or up to Grade 1 per DMID Toxicity Tables), as deemed by the Investigator. Note: Lab results within the testing facility's normal range will not be considered AEs when referenced to the DMID assessment/grading scale. If exclusionary lab criteria are met, values may be confirmed by repeat evaluation.
- 5. Has not used tobacco- or nicotine-containing products (including smoking cessation products), for a minimum of 6 months before dosing.
- 6. If female of non-childbearing potential, she has undergone one of the following sterilization procedures at least 6 months before dosing:
 - Hysteroscopic sterilization;
 - Bilateral tubal ligation or bilateral salpingectomy;
 - Hysterectomy; or
 - Bilateral oophorectomy;
 - Or is postmenopausal with amenorrhea for at least 1 year before the first dose with serum FSH levels consistent with postmenopausal status (i.e., greater than 40 mIU/mL) at screening.
- 7. If female of childbearing potential, must be using effective birth control methods, as defined below and is willing to continue practicing birth control methods and not planning to conceive throughout treatment until after the last follow-up visit (or until at least 12 weeks [male participants] or 6 weeks [female participants] after the date of early withdrawal). The following are allowed birth control methods for this study:

- Double barrier method (e.g., diaphragm with spermicide; condoms with spermicide);
- Intrauterine device (IUD);
- Abstinence (and must agree to use a double barrier method if they become sexually active during the study);
- Vasectomized partner (at least 6 months before dosing);
- Non-surgical permanent sterilization (e.g., Essure® procedure) at least 3 months before dosing;
- Implanted or intrauterine hormonal contraceptives in use for at least 6 consecutive months before study dosing; and/or
- 8. If a non-vasectomized male (or male vasectomized less than 120 days prior to study start) he must agree to the following during study participation and for 90 days after the last follow-up visit (or until at least 90 days after the date of early withdrawal):
 - Use a condom with spermicide while engaging in sexual activity or be sexually abstinent; and
 - Not donate sperm during this time.

In the event the sexual partner is surgically sterile or postmenopausal, use of a condom with spermicide is not necessary. None of the birth control restrictions listed above are required for vasectomized males whose procedure was performed more than 120 days before study start.

- 9. Is willing to answer inclusion and exclusion criteria questionnaire at check-in.
- 10. Is able to comply with the protocol and the assessments therein, including all restrictions.
- 11. Is willing and able to remain in the study unit for the entire duration of the assigned confinement period and return for outpatient visits.
- 12. If assigned to receive study drug under fed conditions, is willing and able to consume the entire high-calorie, high-fat breakfast meal in the timeframe required.

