		tartrate. The composition of the tablets is as follows: lactose monohydrate, microcrystalline cellulose, povidone, crospovidone, colloidal silicon dioxide, and magnesium stearate. The formulation of the two strengths of tablets is identical and dose proportional.
		Add the following to the end of Container and Closure System:
		TBAJ-876 Tablets 25 mg are packaged as 30-count in 30 cc round high-density polyethylene (HDPE) bottles induction sealed and with 28 mm polypropylene (PP) child resistant closures (CRC). TBAJ-876 Tablets 100 mg are packaged as 30-count in 40 cc round HDPE bottles induction sealed and with 33 mm PP CRC. The tables are stored at 15-30 °C (59-86 °F).

PROTOCOL SYNOPSIS

Name of Sponsor/Company: Global Alliance for TB Drug Development

Name of test product: TBAJ-876

Name of active ingredient: TBAJ-876 Tartrate

Title of study: A Phase 1, Partially Blind, Placebo Controlled, Randomized, Combined Single Ascending Dose with a Food Effect Cohort (Part 1), Multiple Ascending Dose (Part 2), and Relative Bioavailability (Part 3) Study to Evaluate the Safety, Tolerability, Pharmacokinetics of TBAJ-876 in Healthy Adult Subjects

Principal Investigator: [name]

Study Center

Worldwide Clinical Trials Early Phase Services, LLC [name]

Study period:

Part 1: Single ascending dose (SAD) cohorts which includes a Food-effect Cohort: approximately 56 days, from Day -1 to study exit.

Part 2: Multiple ascending dose (MAD) cohorts: approximately 133 days, from Day -1 through completion of clinical procedures on Day 126 followed by a phone call on Day 133.

Part 3: Single dose, open-label parallel relative bioavailability (BA) design: approximately 45 days, from Screening to study exit.

The maximum duration of the study will depend upon the final number and timing of each cohort and the observed terminal half-life $(T_{1/2})$.

Duration of treatment:

Part 1: One single dose of TBAJ-876 Oral Suspension or placebo for TBAJ-876 Oral Suspension

Food-effect Cohort: One single dose of TBAJ-876 Oral Suspension. Subjects will receive TBAJ-876 Oral Suspension in fasted or fed conditions.

Part 2: Multiple doses (14 doses per cohort) of TBAJ-876 Oral Suspension or placebo for TBAJ-876 Oral Suspension

Phase of development: 1

Number of sites enrolling subjects: 1

Part 3: One single dose of 100 mg TBAJ-876 as 1 x 100 mg tablet (either fasted or fed) or 4 x 25 mg tablets (fasted).

Number of subjects (planned):

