3 STUDY DESIGN SUMMARY

This study is a three-part, partially blinded, placebo controlled, combined single ascending dose (SAD) with food-effect, multiple ascending dose (MAD) study, and a single dose relative bioavailability (BA) study conducted in one study center in the United States.

Safety will be assessed throughout the study for all subjects. Safety assessments will include physical examinations, vital signs, serial ECGs, cardiac monitoring, adverse events (AEs), and clinical laboratory tests (including hematology, serum chemistry, coagulation, and urinalysis).

Part 1:

Part 1 is a SAD design with 6 planned dose levels. Additional cohorts may be enrolled if deemed appropriate by the Sponsor to repeat a dose level or study another dose level. Interim PK analyses and safety assessments will be performed for the dose escalation decisions and to select the dose level at which to assess the food-effect. The food-effect cohort is planned with two parallel groups, one fasting and the other fed.

Current duration and scheduling of safety and PK sampling assumes that the terminal half-life ($T_{1/2}$) will be approximately 7 days. The number and timing of PK sampling and safety assessments may be further revised based on evolving PK and safety information.

Subjects will be housed in the clinic from at least 24 hours prior (from Day -1), until 7 days after dosing (Day 8).

Subjects from Dose Level 1 will return to the clinic to have subsequent follow up safety (collection of AEs) and PK assessments on Days 10, 14, 17, 21, and 28.

Food-Effect: Based on exposure levels from the first 4 completed cohorts, the 100 mg dose was chosen for the food-effect cohort. In this food-effect cohort, there will be two parallel groups, one fasting and the other fed. The fed group will enroll at least 10 subjects and the fasted group will include data from 6 subjects who completed Cohort 4 and at least 3 additional subjects who will be enrolled in the fasted group. All subjects in the food-effect cohort will receive active drug of TBAJ-876, 100 mg.

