6.4 Confinement

For Part 1, subjects will be admitted to the research center on Day -1 and remain in the research center until completion of the procedures on Day 8. Subjects will return for subsequent follow up visits on Days 10, 14, 17, 21, and 28. Available subjects from

Cohorts 4 and 5, and all subjects in Cohort 6 will also return bi-weekly (+/- 2 days) up to 10 weeks or longer postdose.

Additional cohort, Cohort 7: Subjects will check-in to the clinic on Day -1 and be confined through Day 8. Subjects will be discharged from the clinic on Day 8. Subjects will return for one follow-up visit on Day 14 for PK and safety. Subjects will receive a follow-up phone call on Day 21.

For Part 2, subjects will be admitted to the research center on the evening of Day -1 and remain in the research center until completion of the procedures on Day 21. Subjects will return for subsequent follow up visits on Days 42, 63, 84, 105, and 126 (+/- 1 day) and will receive a phone call on Day 133 (+/- 1 day).

For Part 3, subjects will be admitted to the research center on the evening of Day -1 and remain in the research center until completion of the procedures on Day 8. Subjects will return for subsequent follow-up visits on Days 10 and 14 and will receive a follow-up phone call on Day 21.

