7.9 Pregnancy

The Investigator will immediately notify the Sponsor of any pregnancy that is discovered during the clinical trial. Pregnancy forms will be completed for all pregnancies reported during the study or in the 30 days after completion of the IMP. In addition, the Investigator will report to the Sponsor follow up information regarding the outcome of the pregnancy, including perinatal and neonatal outcome. Infants should be followed for 6 months.

If pregnancy is suspected while the subject is receiving IMP, the IMP will be withheld immediately until the result of the pregnancy test is known. If pregnancy is confirmed, the IMP will be permanently discontinued in an appropriate manner and the subject withdrawn from the trial. Protocol-required procedures for trial discontinuation and follow up will be performed unless contraindicated by the pregnancy.

If the Investigator becomes aware the female partner of a male subject becomes pregnant during the study or in the 30 days after the completion of IMP, consent will be requested from the female partner for collection of information on her pregnancy history and for information on the current pregnancy and birth.

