- f. Vital signs (blood pressure, pule rate, temperature, respiration rate, and pulse oximetry) will measured at screening and check-in (Day -1). Vital sign measurements will be taken within 90 minutes prior to dosing and within 15 minutes of the defined time points at study hours 0, 1, 6, and 12 on Days 1 and 14. Furthermore, vital signs will also be taken once daily on Day 2 through Day 14 (6 hours after dosing) and once daily on Days 15-21 and Days 42, 63, 84, 105, and 126 and at early withdrawal (to be done within 15 minutes before review of medication and collection of adverse experiences). Both blood pressure and heart rate will be captured simultaneously. Blood pressure and heart rate will be measured after subjects are in a seated position for 2 minutes and then again after standing for 1 minute, except when they are supine or semi-reclined because of study procedures and/or adverse events, or as deemed necessary by the Investigator.
- g. AEs will be monitored from the time of signing the informed consent throughout the study via safety assessments, observation and participant reporting. Specific AE questions will be posed daily throughout the study until Day 21 and on all follow-up visits including a phone call on Day 133.
- h. TBAJ-876 or Placebo to TBAJ-876 Oral Suspension will be administered orally followed by 240 mL of water. Listerine® strips will be used as a blinding agent. A strip will be added to the subject's tongue before and after each dose.

Global Alliance for TB Drug Development

CONFIDENTIAL

- Dosing will only occur on Days 1-14.
- j. 12-lead safety ECGs will be printed and reviewed on-site by the Principal Investigator or designee. Triplicate ECGs will be completed at screening, Day -1, and on Day 15 or upon early withdrawal. All other time points will be single ECG readings. ECGs may be done within 2 hours prior to time of dosing and at 6 hours after dosing on Days 1, 2, 3, 8, 12, 14, and on Days 21, 42, 63, 84, 105, and 126. The predose ECG will be completed within 1 hour prior to the predose blood draw. If a participant experiences a postdose QTcF >500 ms or a change-from-baseline QTcF >60 ms, after repeat testing, additional ECGs should be recorded until normalization or return to baseline. All ECGs in Cohort 3 will be triplicate at each time point. In addition, subjects in Cohort 3 will have triplicate ECGs at 16 hours postdose on Day 1 and Day 14.
- k. Predose trough plasma samples will be drawn daily Days 1 through 14.

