- c. Vital signs (blood pressure, pule rate, temperature, respiration rate, and pulse oximetry) will be measured at screening and check-in (Day -1). Vitals signs will be measured within 90 minutes prior to dosing and within 15 minutes of the defined time points. Both blood pressure and pulse rate should be captured simultaneously. Blood pressure and pulse rate will be measured after subjects are in a seated position for at least 2 minutes and then again after standing for 1 minute, except when they are supine or semi-reclined because of study procedures and/or AEs, or as deemed necessary by the Investigator.
- d. 12-lead safety ECGs will be printed and reviewed on-site by the Principal Investigator or designee. Triplicate ECGs will be completed at screening, Day -1, each time point listed, and on Day 8 or upon early withdrawal. ECG readings will be within 15 minutes of the time points. The first ECG Day 1 may be done within 2 hours prior to dosing and must be completed 20 minutes prior to the predose blood draw. All safety ECGs on Day 1 and Day 2 will be extracted from a continuous 12 lead Holter recording at discrete timepoints as noted in above flow chart. If a subject experiences a postdose QTcF >500 msec or a change-from-baseline QTcF >60 msec, after repeat testing, additional ECGs will be recorded until normalization or return to baseline.
- e. Safety laboratory assessments will be done at check-in (Day -1), 6 and 48 hours postdose and on Days 5, 7, 10, and 14. The following analyses will be performed:

Global Alliance for TB Drug Development

CONFIDENTIAL

^{*} Subjects will return for follow-up visits on Day 10 and 14. Subjects will receive a follow-up phone call on Day 21.

- Full blood cell count (hemoglobin, hematocrit, red blood cell count, white blood cell count with differential, reticulocyte count, platelet count), reticulocyte count
- Coagulation Tests: Activated partial thromboplastin time (aPTT2), Prothrombin time (PT2)
- Clinical Chemistry (albumin, serum urea, creatinine, direct, indirect, and total bilirubin, uric acid, total protein, alkaline phosphatase, aspartate aminotransferase (AST), alanine aminotransferase (ALT), phosphate, sodium, potassium, calcium (corrected for albumin), chloride, magnesium, glucose, bicarbonate/CO2, creatine phosphokinase (CPK), creatine phosphokinase myocardial band (CPK-MB), lipase, and amylase
- Other laboratory tests: cardiac troponin I and glycosylated hemoglobin

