- Urinalysis (pH, specific gravity, protein, glucose, micro-albumin, ketones, bilirubin, creatinine, nitrite, sodium, urobilinogen, myoglobin, blood, leukocytes). If protein, occult blood, nitrite, or leukocyte esterase values are out of range, a microscopic examination will be performed. Myoglobin will be collected but results will not be required for dose qualification.
- f. Female subjects will have a urine pregnancy test at the end-of-study on Day 14 or early withdrawal.
- g. Subjects will be monitored from the time of signing the informed consent and throughout the study via safety assessments, observation and subject reporting. A specific inquiry regarding AEs will be conducted prior to dosing and at time points specified postdose and upon return to clinic for subsequent visits.
- h. TBAJ-876 Tablet will be administered orally with 240 mL of water.
- i. Subjects will be followed up for safety and PK during follow-up at the following timepoints: pre-dose, 0.5, 1, 2, 3, 4, 5, 6, 8, 10, 12, 16, 20, 24, 28, 32, 36, 40, 44, 48, 54, 60, 66, 72, 80, 88, 96, 120, 144, and 168 hours after dosing, then on Days 10 and 14.
- j. Continuous 12-lead Holter recording (cardiac telemetry) will begin 1 hour before and end 24 hours after dosing.
- k. ECGs on Day 1 will be extracted from a continuous 12 lead Holter recording at discrete timepoints as noted in above flow chart and will be extracted at the same time as vital sign measurements. If a subject experiences a post-dosing QTcF >500 msec or a change-from-baseline QTcF >60 msec, after repeat testing, additional ECGs should be recorded until normalization or return to baseline. NOTE: when ECG extractions coincide with safety ECGs, vital sign assessments, and/or blood draws, then procedures should be carried out in said order.

Global Alliance for TB Drug Development

CONFIDENTIAL

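### Inclusion criterion 7 sets no minimum period of contraception after dosing for women who complete: in Part 3 the duty ends 13 days after the dose (20 if the Day 21 call counts), while women who withdraw must continue for at least 6 weeks

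*Protocol*

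**What the plan says.** Criterion 7 (Protocol 5.1) applies to women of childbearing potential. Contraception must continue "until after the last follow-up visit (or until at least 12 weeks [male participants] or 6 weeks [female participants"; both week counts run from the day on which a subject withdraws early. The rule therefore has two routes: completers stop after the last follow-up visit, and withdrawals continue for a stated number of weeks. Only the second route carries a number.

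Criterion 8, for men, puts the same 90 days on both routes, counted from the last follow-up visit or from early withdrawal.

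The Part 3 schedule in Protocol 6.4 reads "Subjects will return for subsequent follow-up visits on Days 10 and 14 and will receive a follow-up phone call on Day 21". Part 1 Cohort 7 likewise has its last visit on Day 14 and a call on Day 21. The standard Part 1 schedule ends on Day 28. Part 2 has its last dose on Day 14, its last visit on Day 126 and a call on Day 133.

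The only other post-dose period that bears on women is in Section 7.9: "Pregnancy forms will be completed for all pregnancies reported during the study or in the 30 days after completion of the IMP". That is a reporting duty and does not require contraception.

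**The concern.** Two women given the same single dose are held to different periods, and in Part 3 the one who completes gets the shorter. Because the completer's period is tied to the visit schedule, any part with short follow-up has short cover automatically. Nothing in the protocol presents this as a decision about contraception.

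The end date itself is also unclear in Part 3. It depends on whether a phone call is a follow-up visit, so a volunteer cannot tell from criterion 7 whether she is agreeing to Day 14 or Day 21.

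At stake is the length of protection against pregnancy after a drug in its first human study. The women affected are those using methods that can stop when the duty stops, mainly double-barrier methods or abstinence.

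**Working it through.** The plan states no number of days for completers, so there is no figure to reproduce. The check is calendar arithmetic.

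**Inputs.** Dosing is on Day 1 in Parts 1 and 3, and the last dose is on Day 14 in Part 2. By the study-day rule in SAP 6.2.5, days after dosing = study day minus day of last dose. Six weeks = 42 days.

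**Completers, days of cover after the last dose**

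| Group | End point | Days |
|---|---|---|
| Part 3, Cohort 7 | Day 14 visit | 14 − 1 = 13 |
| Part 3, Cohort 7 | Day 21 call | 21 − 1 = 20 |
| Part 1 groups ending on Day 28 | Day 28 visit | 28 − 1 = 27 |
| Part 2 | Day 126 visit | 126 − 14 = 112 |

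SAP 6.2.11 labels the Part 3 Day 14 sample as 336 h, which would make 13 days into 14. The conclusion is the same.

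**Withdrawals.** Cover after a single dose = (withdrawal day − 1) + 42. For withdrawal on Day 10 this is 9 + 42 = 51 days. The excess over a Part 3 completer is 51 − 13 = 38 days, or 51 − 20 = 31.

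**Which end point applies in Part 3.**
- For Day 14: Section 6.4 separates visits from the call; the Table 17 follow-up footnote says "Subjects will return for follow-up visits on Day 10 and 14"; and footnote f says "Female subjects will have a urine pregnancy test at the end-of-study on Day 14 or early withdrawal".
- For Day 21: the follow-up column of Table 17 lists Days 10, 14 and 21. For Part 2, Table 16 footnote g counts a call among the visits: "on all follow-up visits including a phone call on Day 133". The Synopsis gives Part 3 as "approximately 45 days, from Screening to study exit". With no Day 0, Day −21 to Day 21 is 42 days and Day −21 to Day 14 is 35, so 45 is nearer the former. This last item is weak evidence, because the Synopsis length for Part 1 (about 56 days from Day −1) does not match a Day 28 exit either.

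The literal reading is Day 14, but the text does not settle it.

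**Effect of a floor of 42 days after the last dose.**
- Added cover for completers: 42 − 13 = 29 or 42 − 20 = 22 days in Part 3; 42 − 27 = 15 days in a cohort followed to Day 28.
- Remaining difference for withdrawal on Day 10: 51 − 42 = 9 days.
- Largest remaining difference, for withdrawal the day before follow-up ends: 12 + 42 − 42 = 12 days if follow-up ends on Day 14; 19 days if Day 21; 26 days in a cohort followed to Day 28.
- Part 2 is unchanged: a completer has 112 days, and a woman who withdraws on Day 14 after her last dose has 42.

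**Half-life, as context only.** Section 3 says: "Current duration and scheduling of safety and PK sampling assumes that the terminal half-life" is about 7 days. On that figure 13 days is 13/7 = 1.9 half-lives, 20 days is 2.9 and 42 days is 6.0. I give no residual percentages; the objection explains why.

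**The case against.** **No harm is shown.** A reader might infer that Part 3 leaves women unprotected while the drug is still present at a level that matters, and that 6 weeks is the safe limit. The documents support neither. They give no contraception threshold for women, and the 6 weeks appears only in the withdrawal clause, without a rationale. This stands, and it limits the point to consistency.

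**The half-life argument is weak.** The 7 days is a planning assumption stated with the Part 1 design. Section 1.5 describes multiexponential disposition in animals, and Sections 3 and 3.1 tie follow-up of 10 weeks or longer (Part 1) and 15 weeks or longer (Part 2) to interim PK. A percentage remaining, worked out from a single exponential, would look more precise than it is; if the half-life is longer, 42 days is also fewer than six half-lives. This stands, so the finding should not rest on it.

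**Two end dates need not be an error.** One criterion serves all parts, including 14-day dosing, and a woman who withdraws may have no later visit to count from. That explains why a separate withdrawal clause exists. It does not explain why the completer has no minimum, when criterion 8 gives men one on both routes. Nor can the 6 weeks simply stand in for missed follow-up in Part 3, where all follow-up after the dose lasts at most 20 days.

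**Section 7.9 is not contradicted.** The contraception duty can end 10 to 17 days before the 30-day reporting window closes (30 − 20 and 30 − 13), but reporting and contraception are different duties.

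**Reach is small.** Cohorts 1 to 6 and the food-effect cohort had been dosed (Sections 1.6 and 1.7), and SAP 3.1 describes Cohort 7's Day 14 sampling in the past tense. IUDs, implants, sterilization and a vasectomized partner would normally carry on regardless. This stands.

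**Our copy has gaps.** The consent pages are not in it, and the list of methods in criterion 7 breaks off. The missing item is probably a method rather than a duration.

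**Conclusion.** The point holds as a cheap improvement, with minor weight. Criterion 7 sets no post-dose minimum for female completers, and no other section of the protocol supplies one. In Part 3 the duty ends 13 days after the dose on the literal reading, or 20 if the call counts, against at least 42 days from the withdrawal date for a woman who leaves early.

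The day counts rest only on the schedules and the SAP's day numbering, so they are firm. The choice of 6 weeks as the floor is a judgment: it reuses the sponsor's own figure, and the documents do not establish it as the right one. The practical gain is for women of childbearing potential among the 30 Part 3 subjects (their number is not given) and for any single-dose cohort added later.

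**What to change.** Reword criterion 7 so that contraception runs to the later of the last follow-up visit and 6 weeks after the last dose or, for early withdrawal, to at least 6 weeks after the withdrawal date. Make the consent form say the same. In Part 3 the 42-day floor passes both Day 14 and Day 21, so the question of whether the call is a visit no longer matters for completers. As tidy-up only, remove the 12-week male period from this female-only criterion, since criterion 8 already covers men.

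**Cost.** One sentence and a consent check, with no added visits, tests or subjects. Part 3 completers carry 22 to 29 more days of contraception, and completers in any added cohort followed to Day 28 carry 15 more. Part 3 has no scheduled contact after Day 21, so the extra weeks rest on the subject's agreement.

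**What it does not do.** It leaves a difference between completers and withdrawals of up to 12, 19 or 26 days, for follow-up ending on Day 14, 21 or 28. It also does not alter Part 2, where the completer already has the longer cover.
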